# 10.2.3 ANALYSIS OF THE SECONDARY ENDPOINT(S)

- Assess complete response by CT at 2 months or PET/CT at 3 months following completion of therapy. This will be compared against historical controls.
- Response correlation with pre-treatment and during treatment radiomics features on PET/CT/MRI:

Radiomics features based on CT, MRI, PET-CT, noted during various imaging scans (pre-treatment, at 4 week of RT, and follow-up scan) will be correlated with the overall oncological response and outcome

Response correlation at 4 weeks and post treatment imaging with clearance of HPV from serum or oral gargle, and RSI/GARD.

 Correlate response and outcome to mathematical models of tumor growth and death dynamics pre-treatment and during treatment: Mathematical models will be generated based on the pattern of tumor growth and response as depicted by tumor volume measurement on various scans. These mathematical models will be validated by correlating with the overall response and oncological outcome

# 10.2.4 Interim Efficacy/Futility Analysis

One interim efficacy/futility analysis will be conducted when the first 49 subjects have completed evaluation of response to the study treatment. If the number of responsive patients is equal to or less than 27, the trial will be stopped for futility. If the number of responsive patients is equal to or greater than 30, the trial will be stopped for efficacy. Otherwise, the trial will continue to the second stage by enrolling 11 additional subjects.

# 10.2.5 Interim Exploratory Data Analysis

When the first 33 subjects (55% of the total planned sample size of 60) will complete the study treatment, an early interim exploratory data analysis will be performed for data on HPV DNA viral load in oral gargle and plasma samples, demographic variables, and basic biometric screening results. This exploratory analysis is a pilot proof-of-concept study to evaluate the feasibility and consistency of HPV DNA detection in salivary and plasma samples. No analysis of primary and secondary safety and efficacy endpoints will be performed in this exploratory data analysis to keep trial integrity.

- Data for the exploratory analysis will be summarized overall using descriptive statistics. Continuous data will be summarized with number of patients (n), mean, median, minimum, maximum, and standard deviation. Categorical data such as gender, race, and ethnicity will be summarized using frequency counts and percentages.
- Cross-tabulation of descriptive statistics of demographic variables and biometric screening results with dichotomized HPV DNA viral load results (presence/absence of HPV DNA) will be made with Chi-square test and twosample *t*-test as appropriate.
- Pearson's correlation coefficient, Spearman's rank correlation coefficient, and Kappa statistics will be calculated along with p-values as summary statistics for the consistency of HPV viral loads and detection results in oral gargle samples and plasma samples.

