#### 5.1 PARTICIPANT INCLUSION CRITERIA

In order to be eligible to participate in this study, an individual must meet all of the following criteria:

- Provision of signed and dated informed consent form
- Stated willingness to comply with all study procedures and availability for the duration of the study
- Male or female, aged  $\geq$  18 years
- Pathologically (histologically or cytologically) proven diagnosis of p16+ or HPV+ squamous cell carcinoma (including the histological variants papillary squamous cell carcinoma and basaloid squamous cell carcinoma) of the oropharynx; cytologic diagnosis from a cervical lymph node is sufficient. Patients with unknown primary (T0) should be both p16 and HPV positive. Clinical evidence should be documented, and may consist of pathology, palpation, imaging, or endoscopic evaluation, and should be sufficient to estimate the size of the primary (for T stage).
- AJCC 8th edition staging T0-2 N0-1 M0 (N1 includes clinical tumor involvement in only 1-5 lymph nodes) Patients with any smoking history are included if N0 or a single involved node size ≤3cm. However, if the number of involved lymph node is ≥2 or any lymph node size >3 cm, only patients with ≤ 10 pack years of smoking is eligible.
- Patients must have clinically or radiographically evident measurable disease at the primary site or at nodal stations.
- CT or MRI performed at least 1 week apart. This can consist of diagnostic imaging and radiation therapy planning imaging.
- No evidence of distant metastases
- ECOG Performance Status 0 to 2

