# **10.2 DESCRIPTION OF STATISTICAL METHODS**

# 10.2.1 GENERAL APPROACH

This protocol is a single arm, phase II design with a primary endpoint of 63% of patients achieving  $a \ge 32\%$  reduction in tumor volume by week 4. This study will test the null hypothesis that the true response rate is equal to or less than a historical control of  $49\%^{11}$  versus the alternative hypothesis that it is greater than 49%.

Based on Fleming's 2-stage group sequential design, a total of 60 subjects will provide approximately 79% power with a type I error rate of 0.1 to detect a true response rate of 63%. The study will enroll subjects in two stages, with 49 subjects in the first stage. One interim efficacy/futility analysis will be conducted when the first 49 subjects have completed the study treatment and response evaluation. If the number of responsive patients is equal to or less than 27, the trial will be stopped for futility. If the number of responsive patients is equal to or greater than 30, the trial will be stopped for efficacy. Otherwise, the trial will continue to the second stage by enrolling 11 additional subjects.

At the final analysis with the total 60 subjects at the second stage, if there are equal to or more than 35 responsive patients, it will be concluded that the null hypothesis is rejected and the study treatment will be promising.

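### The interim HPV analysis judges gargle–plasma consistency by correlation and kappa with p-values against zero, and plans no interval, percent agreement or paired table that would show the degree of agreement

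*Combined protocol and SAP*

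**What the plan says.** Section 10.2.5 sets the timing: "When the first 33 subjects (55% of the total planned sample size of 60) will complete the study treatment". It describes the work in these terms: "This exploratory analysis is a pilot proof-of-concept study", intended to "evaluate the feasibility and consistency of HPV DNA detection in salivary and plasma samples". Primary and secondary endpoints are kept out of it.

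The third bullet gives the method for consistency. After naming the Pearson and Spearman coefficients it continues: "Kappa statistics will be calculated along with p-values as summary statistics for the consistency of HPV viral loads and detection results", in the two fluids. The coefficients are therefore reported, with p-values beside them.

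The only cross-tabulation in the section is a different one: "Cross-tabulation of descriptive statistics of demographic variables and biometric screening results with dichotomized HPV DNA viral load results (presence/absence of HPV DNA"). A table of gargle result against plasma result is not mentioned. Nor is a confidence interval, a percent agreement, an alpha level, a criterion for calling the fluids consistent, or the visit at which the samples are paired. Sections 7.2.4 and 7.2.5 schedule both fluids at pre-therapy, week 2, week 4 and end of treatment, and again in follow-up, so each patient can contribute several pairs. Section 10.2.3 does not fill these gaps.

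**The concern.** Consistency is a question about degree: in how many patients do the two fluids give the same answer, and how close are the loads? The default p-value for Pearson or Spearman tests a true correlation of zero. The p-value for kappa tests agreement no better than chance. Two samples taken from the same patient can easily be related without agreeing well, so a small p-value leaves the stated question open. Pearson and Spearman have a further limit for viral load: both ignore a constant difference between fluids.

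Kappa does measure agreement, but it depends on how common detection is. Section 5.1 requires "proven diagnosis of p16+ or HPV+ squamous cell carcinoma", so high pre-therapy detection in both fluids is possible, although the documents give no detection rates. In that case kappa can sit near zero while almost all pairs agree.

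What is at stake is whether the look can answer its own question. The HPV-clearance objective in sections 3.2 and 10.2.3 uses the same kinds of specimen, so a clear description of agreement would help in reading it, though its analysis does not depend on this bullet.

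**Working it through.** **Inputs.** From 10.2.5: n = 33, given as 55% of 60, and 33/60 = 0.55 as stated. Assumed: one pair per patient and a two-sided 5% test. Detection rates are also assumed and shown as a range. Tables are written as both positive / gargle only / plasma only / both negative.

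**1. Correlation.** The smallest significant |r| is t/√(n − 2 + t²), with t = 2.040 on 31 df: 2.040/√(31 + 4.160) = 0.344, and 0.344² = 0.118. The Fisher-z 95% interval at r = 0.344 is about 0.00 to 0.61. At r = 0.40 it is 0.07 to 0.65.

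**2. Correlation against agreement in viral load.** Suppose log10 load has SD 1 in one fluid, and the other fluid equals it plus a constant shift plus noise of SD 0.3.
- r = 1/√1.09 = 0.96 whatever the shift.
- The concordance correlation is 2/(1 + 1.09 + shift²).
- For a tenfold difference (shift 1) it is 2/3.09 = 0.65. For a 100-fold difference (shift 2) it is 2/6.09 = 0.33.

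**3. Kappa with moderate detection.** Kappa = (po − pe)/(1 − pe), where po is observed and pe is chance agreement. The test is z = kappa divided by its large-sample standard error under kappa = 0. With 50% detection in each fluid, pe = 0.50. Summing the exact probabilities of all tables with n = 33 that have kappa > 0 and p < 0.05 gives:

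| True kappa | Patients discordant | Probability of p < 0.05 |
|---|---|---|
| 0.3 | 35% | 0.41 |
| 0.4 | 30% | 0.65 |
| 0.5 | 25% | 0.85 |

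A single example is 9/15/0/9. Here po = 18/33 = 54.5%, pe = 2 × (24/33) × (9/33) = 0.397 and kappa = 0.25, with p = 0.031.

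**4. Kappa with very high detection.** In the table 31/1/1/0, po = 31/33 = 93.9% and pe = (32/33)² + (1/33)² = 0.941, so kappa = −0.03 with p = 0.86.

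For 95% detection in each fluid and 92% true agreement, the cell probabilities are 0.91, 0.04, 0.04 and 0.01.
- Chance agreement is 0.95² + 0.05² = 0.905, so true kappa is (0.92 − 0.905)/0.095 = 0.16.
- Kappa is undefined when every pair is positive in both fluids: 0.91³³ = 0.045.
- Its test cannot be computed when at least one fluid is all positive: 2 × 0.95³³ − 0.91³³ = 0.368 − 0.045 = 0.32. In most of those trials kappa exists and equals 0, but its null standard error is zero.

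**5. What agreement measures show.** Overall agreement with exact (Clopper–Pearson) 95% intervals is 31/33 = 93.9% (79.8% to 99.3%) in the step 4 table. It is 18/33 = 54.5% (36.4% to 71.9%) in the step 3 table. The p-values, 0.86 and 0.031, put these two tables in the opposite order.

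**The case against.** The best defence is that the coefficients are reported, so a reader who sees kappa of 0.25 or r of 0.35 would not call the fluids consistent merely because p is below 0.05. The section states no alpha and no decision rule, labels the work an exploratory pilot, and keeps the trial's endpoints out of it. All of this stands, and it limits the importance of the point. It does not supply the missing precision: a coefficient from 33 pairs without an interval is hard to interpret, and r and rho do not measure agreement.

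Three stronger readings are tempting.

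- A reader might infer that the plan will declare consistency when p < 0.05. No such rule is written.
- A reader might infer that the test favours weaker agreement over stronger, because it is significant in 65% of trials at 70% raw agreement (step 3) but in about 23% at 92% (step 4). That ordering holds only for raw agreement. True kappa is 0.40 in the first case and 0.16 in the second, so the test follows kappa. The reversal comes from kappa's dependence on prevalence, not from its p-value.
- A reader might infer that high detection is expected. The tumour criterion accepts p16 positivity alone except in T0 disease, and it says nothing about detection in gargle or plasma. That case remains conditional.

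**Conclusion.** The point holds as a mismatch between the stated purpose and the planned summaries. Section 10.2.5 asks about consistency, but its p-values address zero association or chance-level agreement. Nothing planned gives the precision of the coefficients, the proportion of patients who agree, or any systematic difference in viral load.

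The threshold of 0.344 rests on n = 33 and an assumed two-sided 5% test. The 65% figure also assumes 50% detection in each fluid. The figures at high detection (test not computable in about 32% of trials, kappa itself undefined in about 4.5%) assume 95% detection in both fluids and 92% agreement, which the documents neither support nor exclude. The viral-load illustration rests on assumed variances and shifts.

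Importance is low to moderate. No stopping or treatment decision uses this analysis, and the primary endpoint is untouched.

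**What to change.** Amend the third bullet of 10.2.5. Replace the p-values with estimates and 95% confidence intervals, using one gargle–plasma pair per patient at each named visit, with pre-therapy first.

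- **Detection:** the paired 2×2 table with both discordant counts; overall agreement; positive and negative percent agreement, with the reference fluid stated so that exact 95% intervals apply; and kappa with a 95% interval beside the detection rate in each fluid. If kappa or its interval cannot be computed, say so and rely on the table and the agreement proportions.
- **Viral load:** Spearman's rho with a 95% interval, labelled as association only. If the two assay scales are comparable, add a concordance correlation or limits of agreement on log viral load.
- **Several visits:** if visits are combined, use a bootstrap that resamples patients, and account for visit.

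Any statement about consistency should rest on the interval for agreement. The cost is a change of wording, with no new samples or data. With 33 patients the intervals will be wide, as the two in step 5 show, and the result will look less decisive than a small p-value.

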# 10.3 SAMPLE SIZE

60 patients total. Total accrual time is expected to be 30 months.

# 11 SOURCE DOCUMENTS AND ACCESS TO SOURCE DATA/DOCUMENTS

The Investigator is responsible for ensuring the source data are accurate, legible, contemporaneous, original, and attributable.

# 12 QUALITY ASSURANCE AND QUALITY CONTROL

Regulatory documents and case report forms will be monitored internally according to Moffitt Cancer Center Monitoring Policies. Monitoring will be performed regularly to verify data is accurate, complete, and verifiable from source documents; and the conduct of the trial is in compliance with the currently approved protocol/amendments, Good Clinical Practice (GCP), and applicable regulatory requirements.

# 13 ETHICS/PROTECTION OF HUMAN SUBJECTS

## 13.1 ETHICAL STANDARD

The investigator will ensure that this study is conducted in full conformity with Regulations for the Protection of Human Subjects of Research codified in 45 CFR Part 46, 21 CFR Part 50, 21 CFR Part 56, and/or the ICH E6.

#### **13.2 INSTITUTIONAL REVIEW BOARD**

The protocol, informed consent form(s), recruitment materials, and all participant materials will be submitted to the IRB for review and approval. Approval of both the protocol and the consent form must be obtained before any participant is enrolled. Any amendment to the protocol will require review and approval by the IRB before the changes are implemented to the study. All changes to the consent form will be IRB approved; a determination will be made regarding whether previously consented participants need to be re-consented.

# **13.3 INFORMED CONSENT PROCESS**

# 13.3.1 CONSENT/ASSENT AND OTHER INFORMATIONAL DOCUMENTS PROVIDED TO PARTICIPANTS

Consent forms describing in detail the study agent, study procedures, and risks are given to the participant and written documentation of informed consent is required prior to starting intervention/administering study product.

# 13.3.2 CONSENT PROCEDURES AND DOCUMENTATION

Informed consent is a process that is initiated prior to the individual's agreeing to participate in the study and continues throughout the individual's study participation. Extensive discussion of risks and possible benefits of participation will be provided to the participants and their families. Consent forms will be IRB-approved and the participant will be asked to read and review the document. The investigator will explain the research study to the participant and answer any questions that may arise. All participants will receive a verbal explanation in terms suited to their comprehension of the purposes, procedures, and potential risks of the study and of their rights as research participants. Participants will have the opportunity to carefully review the written consent form and ask questions prior to signing.

The participants should have the opportunity to discuss the study with their surrogates or think about it prior to agreeing to participate. The participant will sign the informed consent document prior to any procedures being done specifically for the study. The participants may withdraw consent at any time throughout the course of the trial. A copy of the informed consent document will be given to the participants for their records. The rights and welfare of the participants will beprotected by emphasizing to them that the quality of their medical care will not be adversely affected if they decline to participate in this study.

# **13.4 PARTICIPANT AND DATA CONFIDENTIALITY**

Participant confidentiality is strictly held in trust by the participating investigators, their staff, and the sponsor(s) and their agents. This confidentiality is extended to cover testing of biological samples and genetic tests in addition to the clinical information relating to participants. Therefore, the study protocol, documentation, data, and all other information generated will be held in strict confidence. No information concerning the study or the data will be released to any unauthorized third party without prior written approval of the sponsor.

The study monitor, other authorized representatives of the sponsor, representatives of the IRB or pharmaceutical company supplying study product may inspect all documents and records required to be maintained by the investigator, including but not limited to, medical records (office, clinic, or hospital) and pharmacy records for the participants in this study. The clinical study site will permit access to such records.

The study participant's contact information will be securely stored at each clinical site for internal use during the study. At the end of the study, all records will continue to be kept in a secure location for as long a period as dictated by local IRB and Institutional regulations.

Study participant research data, which is for purposes of statistical analysis and scientific reporting, will be transmitted to and stored at the Coordinating Center. This will not include the participants' contact or identifying information. Rather, individual participants and their research data will be identified by a unique study identification number. The study data entry and study management systems used by clinical sites and by the Coordinating Center research staff will be secured and password protected. At the end of the study, all study databases will be de-identified and archived at the Coordinating Center.

# 13.5 FUTURE USE OF STORED SPECIMENS

Data collected for this study will be analyzed and stored at the Moffitt Cancer Center.

# 14 DATA HANDLING AND RECORD KEEPING

## 14.1 DATA COLLECTION AND MANAGEMENT RESPONSIBILITIES

Data collection is the responsibility of the clinical trial staff at the site under the supervision of the site PI. The investigator is responsible for ensuring the accuracy, completeness, legibility, and

timeliness of the data reported.

All source documents should be completed in a neat, legible manner to ensure accurate interpretation of data. Black ink is required to ensure clarity of reproduced copies. When making changes or corrections, cross out the original entry with a single line, and initial and date the change. DO NOT ERASE, OVERWRITE, OR USE CORRECTION FLUID OR TAPE ON THE ORIGINAL.

Copies of the electronic CRF (eCRF) will be provided for use as source documents and maintained for recording data for each participant enrolled in the study. Data reported in the eCRF derived from source documents should be consistent with the source documents or the discrepancies should be explained and captured in a progress note and maintained in the participant's official electronic study record.

Clinical data (including AEs, concomitant medications, and expected adverse reactions data) and clinical laboratory data will be entered into <specify name of data capture system>, a 21 CFR Part 11-compliant data capture system provided by Moffitt Cancer Center. The data system includes password protection and internal quality checks, such as automatic range checks, to identify data that appear inconsistent, incomplete, or inaccurate. Clinical data will be entered directly from the source documents.

## 14.2 STUDY RECORDS RETENTION

Study documents should be retained for a minimum of 2 years. These documents should be retained for a longer period, however, if required by local regulations. No records will be destroyed without the written consent of the sponsor, if applicable. It is the responsibility of the sponsor to inform the investigator when these documents no longer need to be retained.

#### 14.3 PROTOCOL DEVIATIONS

A protocol deviation is any noncompliance with the clinical trial protocol, GCP or MOP requirements. The noncompliance may be either on the part of the participant, the investigator, or the site study staff. As a result of deviations, corrective actions are to be developed by the site and implemented promptly.

These practices are consistent with ICH E6:

- 4.5 Compliance with Protocol, sections 4.5.1-3
- 5.1 Quality Assurance and Quality Control section 5.1.1
- 5.2 Noncompliance, sections 5.20.1-2

It is the responsibility of the site to use continuous vigilance to identify and report deviations within 10 working days of identification of the protocol deviation, or within 10working days of the scheduled protocol-required activity. All deviations must be addressed in study source documents, reported to protocol monitoring committee. Protocol deviations must be sent to the local IRB per their guidelines. The site PI/study staff is responsible for knowing and adhering to their IRB requirements. Further details about the handling of protocol deviations will be included in the MOP.

## 14.3 PUBLICATION AND DATA SHARING POLICY

The study of these patients and results are considered private and confidential. The progress and results of this study will not be presented without approval by the principal investigator.

# 15 STUDY ADMINISTRATION

#### 15.1 STUDY LEADERSHIP

Not applicable.

## 16 CONFLICT OF INTEREST POLICY

The independence of this study from any actual or perceived influence, such as by the pharmaceutical industry, is critical. Therefore any actual conflict of interest of persons who have a role in the design, conduct, analysis, publication, or any aspect of this trial will be disclosed and managed. Furthermore, persons who have a perceived conflict of interest will be required to have such conflicts managed in a way that is appropriate to their participation in the trial. The study leadership in conjunction with the study sponsor has established policies and procedures for all study group members to disclose all conflicts of interest and will establish a mechanism for the management of all reported dualities of interest.

